### 7.3.4 Safety analyses

Safety will be assessed as defined by the endpoints listed in Section [2.1.2](#) and [2.2.2](#) based on the treated set (TS). Safety analyses will be descriptive in nature and will be based on BI standards.

Proprietary confidential information © 2021 Boehringer Ingelheim International GmbH or one or more of its affiliated companies

For all analyses the treatment actually administered (= treatment at onset) to the subject will be used (any deviations from the randomised treatment will be discussed in the minutes of the Report Planning Meeting).

Treatments will be compared in a descriptive way. The placebo group in the safety evaluation will consist of all subjects treated with placebo, regardless of the dose group in which they were treated. The test treatment groups will be compared to the placebo group in a descriptive way. Tabulations of frequencies/proportions will be used for the evaluation of categorical (qualitative) data, and tabulations of descriptive statistics will be used to analyse continuous (quantitative) data.

Measurements (such as ECGs, vital signs, or laboratory parameters) or AEs will be assigned to treatments (see Section [4.1](#)) based on the actual treatment at the planned time of the measurement or on the recorded time of AE onset (concept of treatment-emergent AEs).

Therefore, measurements planned or AEs recorded prior to intake of trial medication will be assigned to the screening period, those between the trial medication intake and end of REP (see Section [1.2.6](#)) will be assigned to the treatment period. Events occurring after the REP but prior to trial termination date will be assigned to 'follow-up'. These assignments including the corresponding time intervals will be defined in detail in the TSAP. Note that AEs occurring after the last per protocol contact but entered before database lock will be reported to Pharmacovigilance only and will not be captured in the trial database.

Additionally, further treatment intervals (called analysing treatments) may be defined in the TSAP in order to provide summary statistics for other than above periods, such as combined treatments, on-treatment totals, or periods without treatment effects (such as screening and post-study intervals).

Adverse events will be coded using the Medical Dictionary for Regulatory Activities (MedDRA). Frequency, severity, and causal relationship of AEs will be tabulated by treatment, system organ class and preferred term. SAEs, AESIs (see Section [5.2.7.1](#)) and other significant AEs (according to ICH E3) will be listed separately.

Previous and concomitant therapies will be presented per treatment group without consideration of time intervals and treatment periods.

Laboratory data will be compared to their reference ranges. Values outside the reference range as well as possibly clinically significant values will be highlighted in the listings. Additionally, differences from baseline will be evaluated.

Vital signs or other safety-relevant data will be assessed with regard to possible on-treatment changes from baseline.

The ECG variables QT, HR, QTcF, QTcB, PR, QRS, and RR obtained from the centralised evaluation of 12-lead ECG recordings will be the basis for the derivation of quantitative and categorical ECG endpoints. These endpoints and their analyses will be described in the TSAP.

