#### 1.4.3.6 Risk minimization (safety precautions and stopping rules)

The following risk minimization measures, including safety precautions and stopping rules, **will be implemented in this study**:

- Careful selection of starting dose, as described in Section [1.3.1](#).
- Decreasing escalation factors with increasing doses, as described in Section [1.3.2](#). Dose escalations will only be allowed after documented interim safety reviews (see Section [3.1](#)).
- Preliminary measurement of BI 1595043 pharmacokinetics ( $C_{max}$ ,  $AUC_{0-24}$ ; see Section [7.3.2](#)). The expected exposure in the next higher dose group will be estimated based on preliminary PK data of preceding dose groups. The next higher dose level will only be administered, if estimated mean values of  $C_{max}$  and  $AUC_{0-24}$  do not exceed the maximum acceptable human exposure (see Section [1.3.2](#)).
- For safety reasons, division of each dose group of 8 subjects (6 on active treatment, 2 on placebo) into 3 staggered cohorts. On the first study day of each dose level, 2 subjects (Cohort 1) will be treated (one with active treatment, the other with placebo). On the second study day, the next 2 subjects (Cohort 2) will be treated (two with active treatment). On the third study day of each dose level, the remaining 4 subjects (Cohort 3) will be treated (three with active treatment, one with placebo). If BI 1595043 was safe and well tolerated in Cohort 1, the study will continue with Cohort 2. If it was safe and well tolerated in the preceding cohorts, the study will continue with Cohort 3. Between the first application of BI 1595043 in each cohort, there will be a time interval of at least 24 h which is expected to cover the peak exposure of the compound. In Cohort 2 and Cohort 3, subjects will be dosed at least 10 min apart.

Proprietary confidential information © 2021 Boehringer Ingelheim International GmbH or one or more of its affiliated companies

- A monitoring of safety laboratory with specific focus on plasma glucose levels and liver enzymes (see [Flow Chart](#)).
- An ECG monitoring including continuous ECG measurement over 4 hours post dose to cover the anticipated period of highest drug exposure and additional repeated triplicate 12-lead ECGs up to 48 hours following drug administration. Dose escalation would be stopped as soon as at least 2 subjects at one dose level showed relevant QT prolongation (see Section [3.3.4.3](#)).

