Substrates	Glucose (Plasma) Creatinine Bilirubin, Total Bilirubin, Direct Protein, Total Albumin Albumin (Protein Electrophoresis) Alpha-1-Globulin (Protein Electrophoresis) Alpha-2-Globulin (Protein Electrophoresis) Beta-Globulin (Protein Electrophoresis) Gamma-Globulin (Protein Electrophoresis) C-Reactive Protein (Quant) Uric Acid Cholesterol, total Triglyceride	X X X X X X X X X X X X X X X X X X	X X X X X X X X X X X X X X X X X X	X X X X X X X X X X X X X X X X X X

A: parameters to be determined at Visit 1 (screening examination)

B: parameters to be determined at Visit 2 on Days -3 to -1, 2, 3 and 5 (for time points refer to [Flow Chart](#))

C: parameters to be determined at Visit 3 (end of trial examination)

Proprietary confidential information © 2021 Boehringer Ingelheim International GmbH or one or more of its affiliated companies

**Table 5.2.4: 1** Routine laboratory tests (cont).

Functional lab group	BI test name [comment/abbreviation]	A	B	C
Electrolytes	Sodium	X	X	X
	Potassium	X	X	X
	Calcium	X	X	X
Urinalysis (Stix)	Urine Nitrite (qual)	X	X	X
	Urine Protein (qual)	X	X	X
	Urine Glucose (qual)	X	X	X
	Urine Ketone (qual)	X	X	X
	Urobilinogen (qual)	X	X	X
	Urine Bilirubin (qual)	X	X	X
	Urine RBC/Erythrocytes (qual)	X	X	X
	Urine WBC/Leucocytes (qual)	X	X	X
	Urine pH	X	X	X
Urine sediment (microscopic examination if erythrocytes, leukocytes nitrite or protein are abnormal in urine)	Only positive findings will be reported (for instance, the presence of sediment bacteria, casts in sediment, squamous epithelial cells, erythrocytes, leukocytes)			

A: parameters to be determined at Visit 1 (screening examination)

B: parameters to be determined at Visit 2 on Days -3 to -1, 2, 3 and 5 (for time points refer to [Flow Chart](#))

C: parameters to be determined at Visit 3 (end of trial examination)

The tests listed in Table [5.2.4: 2](#) are exclusionary laboratory tests that may be repeated as required. The results will not be entered in the CRF/database and will not be reported in the CTR. Drug screening will be performed at screening and after admission to the trial site. Infectious serology will be performed at screening only.

**Table 5.2.4: 2** Exclusionary laboratory tests

Functional lab group	Test name
Drug screening (urine)	Amphetamine/MDA
	Barbiturates
	Benzodiazepine
	Cannabis
	Cocaine
	Methadone
	Methamphetamines/MDMA/XTC
	Opiates
	Phencyclidine
	Tricyclic antidepressants
Infectious serology (blood)	Hepatitis B surface antigen (qualitative)

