6. GENERAL ANALYSIS DEFINITIONS

6.1 TREATMENT(S)

It was planned that 64 healthy male subjects will enter the study (8 per dose group, 6 on active and 2 on placebo).

For details of dosage and formulation see Table 6.1:1 below.

Table 6.1: 1 Labels for treatments for use in the CTR

Treatment	Short label
P	Placebo
A	BI 1mg
B	BI 3mg
C	BI 6mg
D	BI 12mg
E	BI 25mg
F	BI 50mg
G	BI 90mg
K	BI 160mg

*: The placebo control group in the safety evaluation will consist of all placebo treated subjects, regardless of the dose group in which they were treated.

The following separate study phases will be defined for the analyses of AEs:

- **Screening** (ranging from 0:00 h on day of informed consent until administration time of study drug)
- **On treatment**
Separately for each treatment, ranging from the time of first administration of BI / Placebo until 0:00h on the day after trial termination date

All AEs until end of trial examination will be considered on treatment.

Displays of AEs will be presented separately for the treatments described in [Table 6.1: 1](#) above.

The following AE displays will be provided in the report:

Section 15.3 and Appendix 16.1.13.1.8 (for ClinicalTrials.gov and EudraCT) of the CTR displays:

In these displays, the on treatment phase will be analysed by dose group (labelled with the name of the study treatment (short label)). Screening will not be included in this analysis. The following total will be provided in addition:

- a total over all on treatment phases included in this analysis ("Total on treatment"; in 16.1.13.1.8)
- a total over all BI treated phases ("BI Total on treatment")

AEs during screening will be listed in Section 16.2, but not tabulated.

Tables of vital signs, laboratory values, and ECG values will present results by the above mentioned screening and on treatment phase.

More details on the technical implementation of these analyses are provided in the Technical TSAP ADS (analysis data set) plan and Data Reviewers guide.

6.2 **IMPORTANT PROTOCOL DEVIATIONS**

Data discrepancies and deviations from the CTP will be identified for all treated subjects.

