6.7 BASELINE, TIME WINDOWS AND CALCULATED VISITS

For the analysis of vital signs the baseline value is defined as the last measurement before trial drug administration.

For laboratory analysis the baseline is defined as the last measurement before trial drug administration.

Unscheduled measurements of laboratory data or vital signs will be assumed to be repeat measurements of the most recent scheduled measurement (e.g. for follow-up or confirmation of a particular value). Therefore, unscheduled measurements will be assigned to the planned time point of the previous scheduled measurement.

Section 6.1 of the CTP: *Exact times of measurements outside the permitted time windows will be documented. The acceptable time windows for screening and end of trial examination are given in the CTP Flow Chart.*

Study measurements and assessments scheduled to occur 'before' trial medication administration on Day 1 are to be performed and completed within a 3 h-period prior to the trial drug administration (including blank values for PK [REDACTED])

The acceptable deviation from the scheduled time for vital signs, ECG, and laboratory tests will be ± 15 min for the first 4 h after trial drug administration, ± 30 min thereafter. Starting from 48 h post-dose a deviation from the scheduled time for vital signs, ECG and laboratory test of ± 120 min is acceptable.

Adherence to time windows will be checked via the consistency check listings at the RPM.

There will be a centralised evaluation of the 12-lead ECG recordings at the time points and for the ECG recordings specified in [Table 6.7: 1](#) below:

Table 6.7: 1 Time schedule of 12-lead ECG recordings for central evaluation

Visit	Day	Planned time [hh:mm] (relative to drug administration)	Study phase	Central evaluation
1	-28 to -1		Screening	Not applicable
2	1	-01:00	Baseline	first single ECG of each of the 3 triplicates
		-00:45		
		-00:30		
		00:30		first single ECG of the triplicate
		01:00		first single ECG of the triplicate
		01:30		first single ECG of the triplicate
		02:00		first single ECG of the triplicate
		02:30		first single ECG of the triplicate
		03:00		first single ECG of the triplicate
		04:00		first single ECG of the triplicate
2	2	06:00		first single ECG of the triplicate
		08:00		first single ECG of the triplicate
		12:00		first single ECG of the triplicate
2	3	24:00		first single ECG of the triplicate
		34:00		first single ECG of the triplicate
3	48:00			first single ECG of the triplicate

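### Unscheduled laboratory and vital-sign values taken soon after dosing receive a pre-dose time point, and Protocol 7.3.4 and SAP 6.1 disagree on their study phase

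*Protocol*

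**What the plan says.** Five places bear on this.

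- Protocol 7.3.4 assigns ECGs, vital signs and laboratory parameters "based on the actual treatment at the planned time of the measurement", while AEs go by recorded onset. It follows that "measurements planned or AEs recorded prior to intake of trial medication will be assigned to the screening period". The section leaves the detailed intervals to the SAP.
- SAP 6.7 regards an unscheduled laboratory or vital-sign value as a repeat of the latest scheduled one, so that "unscheduled measurements will be assigned to the planned time point of the previous scheduled measurement".
- SAP 6.1 ends screening, and starts the on-treatment phase, at the time of administration. It introduces these phases for AEs and then extends them: "Tables of vital signs, laboratory values, and ECG values will present results by the above mentioned screening and on treatment phase".
- Protocol 5.2.4 (Table 5.2.4: 1) gives the Visit 2 safety laboratory as "parameters to be determined at Visit 2 on Days -3 to -1, 2, 3 and 5". In the Flow Chart the post-dose samples are at 24, 48 and 96 h. The admission entry on Day 1 is only a urine drug screen and an alcohol breath test (footnote 5). The Day -3 to -1 visit can be skipped if screening falls on those days (footnote 7).
- SAP 7.8.3 computes vital-sign statistics per planned time point, using the last value that sits at that time point or was assigned to it.

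SAP 4 declares no change from the protocol's planned analyses.

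**The concern.** The reasoning behind SAP 6.7 is that an unscheduled value follows up or confirms the scheduled one before it. That fails when dosing lies between the two, because a post-dose result cannot confirm a pre-dose result.

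The window matters for safety. Protocol 1.4.3.6 separates cohorts by an interval of "at least 24 h which is expected to cover the peak exposure of the compound" and asks for laboratory monitoring with attention to glucose and liver enzymes. Protocol 5.2.7.1.4 foresees an unscheduled blood test when symptoms suggest hepatic injury. Since no safety laboratory is scheduled on Day 1 after dosing, an unscheduled test is the only laboratory evidence for that period. If it is tabulated at a pre-dose time point or in the screening phase, an early abnormality can drop out of the on-treatment display.

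**Working it through.** **Inputs.** Scheduled laboratory times relative to dosing: between -72 and -24 h, then 24, 48 and 96 h (Flow Chart; Table 5.2.4: 1). Vital signs: a pre-dose reading at about -1 h, and the first post-dose reading at 0:30 (Flow Chart).

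**Rules written out.** Let t be the actual time of an unscheduled value, with dosing at 0, and S the set of scheduled times.

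- SAP 6.7: assigned planned time P(t) = the largest s in S with s ≤ t.
- Protocol 7.3.4: screening if P(t) < 0, otherwise treatment.
- SAP 6.1: screening if t < 0, otherwise on treatment.

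The two phase rules disagree exactly when t ≥ 0 and P(t) < 0, that is, from dosing until the first scheduled post-dose measurement.

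**Laboratory.** The result is the same whether the pre-dose sample is placed at -72 h or at -24 h.

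| Actual time after dosing | P(t) | Protocol 7.3.4 | SAP 6.1 |
|---|---|---|---|
| 0.25, 1, 6, 12, 23.9 h | Day -3 to -1 | screening | on treatment |
| 24.5, 30 h | 24 h | treatment | on treatment |

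The disagreement covers 0 to 24 h. If the Day -3 to -1 visit is omitted, P(t) is the screening visit and the first row is unchanged. The scheduled 24 h sample is not affected, because even if drawn up to 30 min early (Protocol 6.1) it keeps its post-dose planned time.

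**Vital signs.** A reading at 0.25 h gets P(t) of about -1 h: screening by Protocol 7.3.4, on treatment by SAP 6.1. From 0:30 onward P(t) is post-dose and the rules agree. Within the first 30 minutes SAP 7.8.3 adds a second effect: the unscheduled reading is the last value assigned to the pre-dose time point, so it replaces the true pre-dose reading in that row.

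**ECG.** SAP 6.7's rule for unscheduled values names only laboratory data and vital signs, and Protocol 5.2.5.1 keeps unscheduled ECGs out of the interval statistics.

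**Size in a table.** The plan gives no figure to reproduce. Assume one subject has a Day 1 unscheduled laboratory abnormality and normal results at every later sample.

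- Active dose group (n = 6): 1/6 = 16.7% becomes 0/6 = 0%.
- Pooled placebo (8 groups × 2 = 16 planned): 1/16 = 6.3% becomes 0/16 = 0%.

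**The case against.** The strongest reply is that the SAP already settles the phase. Protocol 7.3.4 delegates the intervals to it. SAP 6.1 sets a limit at the time of administration and applies its phases to the laboratory and vital-sign tables. SAP 6.7 speaks of time points and never of phase. On that reading a 6 h value is on treatment, and the screening result appears only by chaining two rules that the documents do not chain themselves.

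Much of this stands. A reader might infer that every unscheduled laboratory test in the first 24 h is classed as pre-treatment. The documents do not support that as a certainty: it follows from Protocol 7.3.4 and is contradicted by SAP 6.1. The reply does not remove the problem, however. The SAP 6.1 phases are introduced for AEs, no sentence says that they override planned-time assignment, and SAP 4 declares no departure from the protocol. Even on the favourable reading, SAP 6.7 still attaches a pre-dose time point to a value that SAP 6.1 calls on treatment.

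A reader might also infer that the rule can only hide drug effects. It relocates placebo values too, and losing a placebo abnormality makes active treatment look worse by comparison.

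The remaining safeguards are real. Clinically relevant changes are recorded as AEs (Protocol 5.2.7.1.1) and placed by onset time. Out-of-range laboratory values are flagged in listings (SAP 7.8.2). Samples at 24, 48 and 96 h still catch changes that persist. Dose escalation rests on the safety reviews in Protocol 3.1, not on these tables. The technical analysis documents and the sponsor's laboratory standard, which SAP 6.1 and 7.8.2 cite, are not available here, so it cannot be seen whether a by-phase abnormality table exists or how unscheduled values enter it.

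**Conclusion.** The point holds as a conflict between passages with a small, specific consequence. SAP 6.7 ties a post-dose unscheduled value to a pre-dose time point for laboratory tests from 0 to 24 h and for vital signs from 0 to 0:30. Protocol 7.3.4 and SAP 6.1 then give different phases for that value. For vital signs, SAP 7.8.3 can also overwrite the pre-dose row.

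The effect is limited to unscheduled values in descriptive tables. Their number is not stated; I assume it is small. The frequencies of 16.7% and 6.3% are illustrations that need an isolated Day 1 abnormality with normal later samples, and a table that counts abnormalities by phase.

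The primary endpoint is not affected, because AEs are placed by onset. Nor is baseline: SAP 6.7 takes the last laboratory or vital-sign measurement before administration, which excludes anything measured after intake. A reader might extend the concern to scheduled pre-dose assessments done late, but that definition keeps them out of baseline, and Protocol 6.1 requires them to be completed before dosing.

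**What to change.** In SAP 6.1 and 6.7, and for consistency in Protocol 7.3.4, state that:

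- laboratory and vital-sign values are assigned to screening or on treatment by actual date and time relative to dosing;
- an unscheduled value taken after intake is never assigned to a pre-dose planned time point. If no scheduled post-dose time precedes it, it is shown as on-treatment unscheduled Day 1 and counted in any on-treatment abnormality display.

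No further sentence on baseline is needed. Confirm that the actual date and time of unscheduled measurements are captured: Protocol 6.1 promises exact times only for measurements outside the permitted windows, and Protocol 5.3.1 specifies clock times only for dosing and PK sampling. The cost is one or two sentences and a small change to the derivation, provided those times are in the database.

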## **7.4 INTERIM ANALYSES**

No interim analysis is planned.

A preliminary analysis of PK parameters (AUC0-24 and Cmax of BI 1595043) provided as individual values and geometric means of all available data from at least 4 subjects on active treatment per current dose level, supported by all the available data from subjects of preceding dose levels, will be performed before proceeding to the next higher dose level. For escalation from dose group 1 to dose group 2, and after the last dose group, preliminary PK data are not required, see Section [3](#).

In contrast to the final PK calculations, the preliminary analysis will be based on planned sampling times rather than on actual times, regardless of whether actual times were within the time windows. Therefore, minor deviations may occur between preliminary and final results. The preliminary analysis will provide individual and mean concentration/effect-time profiles and summary statistics of individual values without subject identification information. The preliminary results will be distributed to the investigator and the trial team.

Depending on the results of available preliminary PK analyses and the tolerability and safety of the compound, changes to the dosing schedule (e.g., additional intermediate doses,) and additional PK/PD preliminary analysis may be performed if requested by the Clinical Trial Lead, the investigator, or Trial Clinical Pharmacokineticist. Preliminary PK results will not be reported in the CTR. No formal preliminary PK report will be written.

No inferential statistical interim analysis is planned. However, after completion of each dose group the investigator (or his or her deputy) is allowed to postpone further dose progression until a preliminary analysis of the data has been performed.

## **7.5 HANDLING OF MISSING DATA**

### **7.5.1 Safety**

It is not planned to impute missing values for safety parameters.

### **7.5.2 Pharmacokinetics**

Handling of missing PK data will be performed according to the relevant Corporate Procedure ([001-MCS-36-472](#)).

PK parameters that cannot be reasonably calculated based on the available drug concentration-time data will not be imputed.

## **7.6 RANDOMISATION**

Each dose group will be divided into three cohorts. The subjects of the first 2 cohorts (2 subjects per cohort) will not be randomized to maintain a treatment sequence of active-placebo (Cohort 1) and active-active (Cohort 2) due to safety reasons. In the third cohort of each dose level (4 subjects) the subjects will be assigned to active or placebo treatment using a 3:1 allocation ratio (test treatment to placebo).

The sponsor will arrange for the randomisation as well as packaging and labelling of trial medication. The randomisation list will be generated using a validated system that uses a pseudo-random number generator and a supplied seed number so that the resulting allocation is both reproducible and non-predictable.

The randomisation list will contain additional blocks to allow for subject replacement (refer to Section [3.3.5](#)).

